## PROTOCOL VERSION 4.0 SUMMARY OF CHANGES TABLE

Document History								
Document:	Date (Day-Month-Year)							
Version 4.0	30 Jun 2020							
Version 3.0	15 Nov 2019							
Version 2.0	03 Oct 2019							
Original Protocol Version 1.0	24 Jul 2019							

#### Amendment: Protocol Version 4.0 (30 Jun 2020)

This amendment is considered to be substantial based on the criteria set forth in Article 10(a) of Directive 2001/20/EC of the European Parliament and the Council of the European Union.

**Overall Rationale for the Amendment:** The overall rationale for this amendment is to incorporate measures into the protocol to ensure the safety of the trial subjects and the validity of the trial data in the environment of the COVID-19 pandemic and to clarify other aspects of trial conduct unrelated to the COVID-19 pandemic.

Section # and Name	Description of Change	Brief Rationale

1.1 Synopsis

3 Objectives and Endpoints

9.4.1 Efficacy Analyses

	Changed the order of the 2 key secondary endpoints	To reflect the sponsor's decision to allow a hierarchical testing sequence

1.1 Synopsis

9.2 Sample Size

Determination

	Added provision to extend enrollment to maintain the planned statistical power in the event of higher than expected early terminations due to COVID-19 or other reasons	Unknown effect of COVID-19 pandemic on trial enrollment
1.3 Schedule of Assessments	Added a footnote to Table 2 to provide an option for specific visits to be completed remotely Added option for COVID-19 testing	To reflect risk assessment measures by sponsor to prioritize trial participant safety
	Deleted portion of footnote in Table 2 about obtaining PK sample at Visit 6	Correct typographical error
2.3 Benefit/Risk Assessment	Added a statement regarding sponsor risk assessment related to COVID-19	To reflect measures implemented by the sponsor to prioritize trial participant safety and data validity

Section # and Name	Description of Change	Brief Rationale

 
5.2 Exclusion Criteria
 
7.3 Individual Subject
 
Discontinuation
 
8.4.6.2 Hematologic
 
Abnormalities
 
	Changed decimal places for WBC and neutrophil counts	Correct typographical errors
5.2 Exclusion Criteria	Modified the wording related to current and prior use of prohibited medications	Simplify language by referring to the respective tables that specify prohibited medications before and during the trial
5.2 Exclusion Criteria 8.3.3 Electrocardiograms	Specify that QTcF interpretation at screening is according to central ECG service reading	Address inconsistency in previous version of the protocol and provide clarification regarding results interpretation
	Align ECG exclusion criterion with methods for obtaining ECGs	
6.7 Intervention after the End of the Trial	Deleted sentence about subjects who require withdrawal from the trial being potentially eligible for entry into the open-label extension trial	Correct error (subjects who do not complete the trial are not eligible for the open-label extension)
8.6 Pharmacokinetics	Simplified wording about sample collection (Sections 8.6.1 and 8.6.2)	Remove duplication of details provided in other materials
	Revised sample analysis wording (Section 8.6.3)	Clarify that only treatment samples will be analyzed
10.1.3 Informed Consent Process	Removed references to legally authorized representative	Correct inconsistency with inclusion criteria
10.2 Appendix 2: Clinical Laboratory Tests	Added section on additional required tests, which includes serum and urine pregnancy tests	Correct inconsistency with Schedule of Assessments
10.3 Appendix 3: Adverse Events: Definitions and Procedures for Recording, Evaluating, Follow-up, and Reporting	Revised section to remove redundant language and to clarify AE and SAE/AESI reporting procedures	Align wording with actual processes that will be followed in trial and for consistency across Cerevel clinical development programs
10.6 Appendix 6: Inducers and Inhibitors of Cytochrome P450 3A	Added eslicarbazepine as CYP 3A inducer	Add to prohibited medications, due to potential for reduction of CVL-865 concentrations
Signature Page	Changes to signatories	Reflect changes in sponsor personnel Reflect consistency of roles across protocols

Section # and Name	Description of Change	Brief Rationale
Overall	Minor grammatical and wording corrections or clarifications throughout protocol	Correct errors in the previous version of the protocol

Abbreviations: AE = adverse event; AESI = adverse event of special interest; CYP = cytochrome P450; ECG = electrocardiogram; PK = pharmacokinetic; SAE = serious adverse event; WBC = white blood cell

# TABLE OF FIGURES

## 1 PROTOCOL SUMMARY

## 1.1 Synopsis

Sponsor Name: Cerevel Therapeutics, LLC

Name of Investigational Medicinal Product: CVL-865

**Protocol Title:** A Randomized, Double-blind, Placebo-controlled, Parallel group, Multicenter Trial of CVL-865 as Adjunctive Therapy in Adults with DRug-REsistAnt FocaL Onset SeIZurEs (REALIZE Trial)

**Short Title:** A Trial of the Efficacy and Safety of CVL-865 as Adjunctive Therapy in the Treatment of Focal Onset Seizures

**IND Number**: 126,900

**EudraCT Number**: 2019-002576-14

**Trial Phase**: 2

Treatment/Indication: Focal Onset Seizures

**Rationale:** This placebo-controlled, double-blind trial is designed to assess the efficacy, safety, and tolerability profile of CVL-865 as adjunctive treatment in subjects with drug-resistant focal onset seizures.

The broad therapeutic use of nonselective benzodiazepines (BZDs) in multiple indications clearly supports the therapeutic potential of  $\gamma$ -aminobutyric acid type A (GABAA) positive allosteric modulators (PAMs) with the potential to offer efficacy with fewer side effects.

A double-blind, placebo-controlled trial is an appropriate design in which to assess initial efficacy with CVL-865. This proof-of-concept trial will assess whether CVL-865 demonstrates efficacy compared with placebo, as measured by a decrease in seizure frequency in subjects with a diagnosis of epilepsy with drug-resistant focal onset seizures.

## **Objectives and Endpoints**

#### Table 1Objectives and Endpoints

Objectives	Endpoints							
Primary: To evaluate the efficacy of CVL-865 as adjunctive therapy compared with placebo in subjects with focal onset seizures	Primary Efficacy: RRatio, defined as RRatio=(T-B)/(T+B) ×100, where T represents the focal onset seizure frequency rate per week in the Maintenance Phase and B represents the focal onset seizure frequency rate per week in the Baseline Period							
	Key Secondary Efficacy:							
	Change from baseline in focal onset seizure frequency per week over the Maintenance Phase							
	• The 50% responder rate, defined as the percent of subjects with at least a 50% reduction in the Maintenance Phase focal onset seizure frequency rate relative to the Baseline Period							
	Other Secondary Efficacy:							
	Seizure freedom							
	Seizure rate over time							
	• PGIC score at Visits 2, 3, and 4							
	• Change from Baseline to Visits 2, 3, and 4 in CGI-S score							
	• CGI-I score at Visit 2, 3, and 4							
	Change from Baseline to Visit 4 in QOLIE-31 Overall score							
	Change from Baseline to Visit 4 in HUI     Utility score							
Secondary (safety): To evaluate the safety and tolerability of CVL-865 in subjects with focal onset seizures	
 
Treatment-emergent adverse events, clinically significant changes in ECGs, vital sign measurements, and physical and neurological examination results
 
							
	Suicidality assessed using the C-SSRS							
	
 
Withdrawal symptoms assessed using the mCIWA-B
 
							
	
 
Nature, frequency, and temporality of TEAEs (nonserious and serious), including abuse-related AEs and AEs related to Medication Handling Irregularities (MHI)
 
							
Secondary (PK): To evaluate the plasma exposure of CVL-865	Summary listing of CVL-865     concentrations by dose and visit							

Abbreviations: AE = adverse event; CGI-I = Clinical Global Impression – Improvement; CGI-S = Clinical Global Impression – Severity of Symptoms; C-SSRS = Columbia-Suicide Severity Rating Scale; ECG =

electrocardiogram; HUI = Health Utilities Index; mCIWA-B = Modified Clinical Institute Withdrawal Assessment – Benzodiazepines; MHI = Medication Handling Irregularities; PGIC = Patient's Global Impression of Change; QOLIE-31 = Quality of Life in Epilepsy-31; RRatio = Response Ratio; TEAE = treatment-emergent adverse event.

### **Overall Design:**

This is a double-blind, parallel-group, placebo-controlled trial with subjects randomized to 1 of the following 3 arms in a 1:1:1 ratio:

- CVL-865 25 mg twice daily (BID) maintenance
- CVL-865 7.5 mg BID maintenance
- Placebo

Subjects who satisfy all inclusion/exclusion criteria and thus are eligible for the trial will be randomly assigned to 1 of the 3 treatment arms at Visit 1, the start of the 13-week Treatment Period (10 weeks for subjects enrolling into the open-label extension trial, see below).

At the completion of the Maintenance Phase in this trial, the investigator will evaluate the subject's eligibility to continue treatment with CVL-865 in the open-label extension trial CVL-865-SZ-002.

**Disclosure Statement:** This is a parallel group treatment trial with 3 arms that are blinded to the subjects and the investigator.

**Number of Subjects:** Approximately 214 subjects will be screened to achieve 150 subjects randomly assigned to treatment (50 per group) and 120 evaluable subjects for an estimated total of 40 evaluable subjects per treatment group.

In the event of higher than anticipated early terminations due to COVID-19 or other reasons, Cerevel may extend enrollment in order to maintain the planned statistical power.

**Key Entry Criteria**: Men and women 18 to 75 years of age, inclusive, with a diagnosis of epilepsy with focal onset (as defined in the 2017 ILAE Classification of Seizures), focal aware (except subjects with only focal aware seizures without a motor component), focal impaired awareness, and focal to bilateral tonic-clonic seizures for at least 2 years prior to signing the ICF will be enrolled into this trial. A history of an average of 4 or more spontaneous and observable focal onset, focal aware, focal impaired awareness, and focal to bilateral tonic-clonic seizures (as defined in previous sentence) per 28-day period for at least 3 months (84 days) prior to signing the ICF along with a minimum of 8 of these seizure types during the 8-week Baseline Period with no 21-day period free of any of these seizure types is also required for entry into the trial.

**Intervention Groups, Trial Treatment, and Duration:** This trial is designed with a maximum duration of approximately 25 weeks. The trial consists of the following:

- 8-week Screening/Baseline Period
- 10- or 13-week Treatment Period, including an initial 2-week Titration Phase, an 8-week Maintenance Phase, and a 3-week Taper Phase (only for subjects not continuing treatment in the open-label extension trial). The tablets (including the number of tablets given) will be the same between the placebo and both CVL-865 dose arms during the Titration, Maintenance, and Taper Phases to maintain the blind. All tablets will be administered orally.
- 4-week Follow-up Period
- The daily dosing schedule will start at Day 1 with a 2-week Titration Phase during which time the subject's dose will be increased in a blinded fashion up to the randomized dose level (CVL-865 25 mg BID, CVL-865 7.5 mg BID, or placebo). In the high-dose group, CVL-865 will be administered as

during the Titration Phase, and then 25 mg BID during the 8-week Maintenance Phase. In the low-dose group, CVL-865 will be administered as during the Titration Phase, and then 7.5 mg BID during the 8-week Maintenance Phase. For subjects not enrolling into the open-label extension trial, following the Maintenance Phase, dose will be gradually decreased over a 3-week Taper Phase.

#### **Statistical Methods:**

A sample size of 50 subjects per group (total of 150 subjects) will provide at least 80% power to detect a difference in the means of the primary outcome measure (RRatio) of -20 (PASS 2008 Tests of Two Means, Two Sample T-Test, 2-sided alpha level = 0.1, Standard Deviation=34, and a 20% dropout rate).

The primary efficacy endpoint is the Rratio over the Maintenance Phase. This is calculated as Rratio= $(T-B)/(T+B) \times 100$ , where T represents the seizure frequency rate per week in the Maintenance Phase and B represents the seizure frequency rate per week in the Baseline Period. The Rratio is between -100 and 100. Negative values will indicate reduction in seizure rate and positive values indicate increase in seizure rate during treatment. Values of Rratio will be analyzed for the modified intent-to-treat population using an analysis of covariance model, including treatment and the baseline seizure frequency per week as a covariate.

## 1.2 Schema

Abbreviations: AED = anti-epileptic drug; BID = twice daily; OLE = open-label extension; Wk = week.

## Figure 1 Trial Schematic

## **1.3** Schedule of Assessments

#### Table 2Schedule of Assessments

	Screening/ Baseline		Treatment Period									Post-treatment Follow-up			
Trial Periods/     Period a Phases     (8 weeks)			Titration Phase (2 weeks)		Maintenance Phase (8 weeks)					Taper Phase (3 weeks)					
Visit/Contact b	Screen- ing	Contact	Visit 1ª	isit 1 a Contact Visit 2 c Contact Visit 3 c Contact Visit 4 d Contact Contact Visit 5 c							ETe	Contact	Visit 6		
Day	-56	-28	1	8	15	29	43	57	71	78	85	92	NA	~99	120
Window	± 3	days						± 3 days							
Entrance and Hist	ory														
Informed consent f	X														
Assign subject identification	X														
Review inclusion/ exclusion criteria	X	Х	Х												
Record medical history	X														
Record seizure history	X														
Head MRI/CT g	X														
Demography	X														
History of drug and alcohol use	X														
Review of birth control methods	X		X	X	Х	Х	Х	Х	Х	Х	Х	Х	Х	X	Х

	Screening/ Baseline Period a (8 weeks)		Treatment Period										Post-treatment Follow-up		
Trial Periods/ Phases			Titration Phase (2 weeks)		Maintenance Phase (8 weeks)				Taper Phase (3 weeks)						
Visit/Contact b	Screen- ing	Contact	Visit 1ª	Contact	Visit 2 c	Contact	Visit 3 c	Contact	Visit 4 d	Contact	Contact	Visit 5 c	ETe	Contact	Visit 6
Day	-56	-28	1	8	15	29	43	57	71	78	85	92	NA	~99	120
Window	± 3	days						± 3 days		•	•				
Complete and send SIF/DRF paperwork to TESC h	x														
Complete Rescue Protocol for subjects who normally receive BZD i	x														
Confirm eligibility based on TESC j			Х												
Randomization			Х												
Dispense eDiary and train on use	х														
Dispense medical bracelet			Х												
Efficacy Assessme	nts														
Review eDiary including compliance with use of eDiary		X	Х	X	x	X	X	X	X	X	X	X	X	X	X
PGIC					X		X		X				X		
CGI-S	ĺ		Х		Х		Х		Х				Х		

Post-treatment Follow-up		ET e Contact Visit 6	NA ~99 120		X	x	x		×	x	x	X X	x x x		^		;
	er Phase veeks)	intact Visit :	85 92						×	x	×	×	x x				\$
	Tape (3 v	Contact Co	78										x				
		Visit 4 d	11		Х	х	x		x	Х	×	х	х				;
t Period	hase	Contact	57	± 3 days													
Treatment	itenance F (8 weeks)	Visit 3 c	43		×					x	x	x					;
	Mair	Contact	29														
		Visit 2°	15		×							×					;
	n Phase eks)	Contact	8														
	Titration (2 we	Visit 1ª	1			x	×			x	×	x					;
/ Baseline	iod a seks)	Contact	-28	lays													
Screening	Peri (8 we	Screen- ing	-56	±3 c					×	x	×	×			$\downarrow$		;
	Trial Periods/ Phases	Visit/Contact b	Day	Window	CGI-I k	QOLIE-31	Health Utilities Index	Safety Assessments	Physical/ neurological examination 	ECG	Vital sign measurements	C-SSRS m	mCIWA-B	Prior/concomitant treatments including BZD use n	Adverse event monitoring n	Laboratory	Safety laboratory

Version 4.0 30 Jun 2020

Confidential

Page 18 of 83

	Screening	o/ Raseline				,	Treatmen	t Period					Post-treatment Follow-up			
Trial Periods/	Per	riod a	Titratio	Titration PhaseMaintenance PhaseTaper Phase					se							
Phases	(8 weeks)		(2 weeks)		(8 weeks)					(3 weeks)						
Visit/Contact b	Screen- ing	Contact	Visit 1ª	Contact	Visit 2 c	Contact	Visit 3°	Contact	Visit 4 d	Contact	Contact	Visit 5°	ETe	Contact	Visit 6	
Day	-56	-28	1	8	15	29	43	57	71	78	85	92	NA	~99	120	
Window	± 3	days				-		± 3 days								
Safety laboratory urine sample	X		Х		X				X				Х			
Serum pregnancy test o	X	<>	Х	<								>	Х	<>	Х	
Serology (HIV, HBV, HCV)	Х															
Urine pregnancy test o					X		Х		Х			Х				
Urine drug screening p	Х															
Blood sample for PK of CVL-865					Xq		X q		X q			X q	Xq			
Blood sample(s) for PK of AED r	X		Х		X		Х		X			Х	X		X	
Future biospecimen research blood sample s			Х													
Other	Other							•								
IMP dispensing			Х		X		Х		X							
Collect final eDiary device															Х	

	Screening	y/ Baseline	Treatment Period									Post-treatment Follow-up			
Trial Periods/ Phases	Period a (8 weeks)		Titration Phase (2 weeks)		Maintenance Phase (8 weeks)					Taper Phase(3 weeks)					
Visit/Contact b	Screen- ing	Contact	Visit 1ª	Contact	Visit 2 c	Contact	Visit 3°	Contact	Visit 4 d	Contact	Contact	Visit 5°	ETe	Contact	Visit 6
Day	-56	-28	1	8	15	29	43	57	71	78	85	92	NA	~99	120
Window	± 3 days			± 3 days											
Provide individualized rescue protocol and train subject i			Х												
IMP compliance assessment					X	X	Х	Х	Х	Х	Х	Х	Х		
Adjunctive AED compliance assessment		Х	Х	х	Х	Х	Х	Х	Х	Х	Х	Х	Х	Х	Х

AED = anti-epileptic drug; BID = twice daily; BZD = benzodiazepine; CGI-I = Clinical Global Impression-Improvement; CGI-S = Clinical Global Impression – Severity of Symptoms; C-SSRS = Columbia-Suicide Severity Rating Scale; CT = computed tomography; ECG = electrocardiogram; ET = Early Termination; HBV = hepatitis B virus; HCG = human chorionic gonadotropin; HCV = hepatitis C virus; HIV = human immunodeficiency virus; ICF = informed consent form; IMP = investigational medicinal product; mCIWA-B = Modified Clinical Institute Withdrawal Assessment – Benzodiazepines; MRI = magnetic resonance imaging; PGIC = Patient Global Impression of Change; PK = pharmacokinetic; QOLIE-31 = Quality of Life in Epilepsy-31; SIF/DRF = Seizure Identification and Diagnostic Review Form; TESC = The Epilepsy Study Consortium.

- a. Individual sites may require subjects to have COVID-19 testing done prior to randomization. COVID-19 testing may be performed after randomization per the investigator's discretion.
- b. Contact with subject via phone call or other means of communication to check on their status.
- c. In the event that a subject is unable to attend a clinic visit in person due to restrictions related to COVID-19, this visit may be completed remotely. Please refer to the Trial Operations Manual for further instructions related to remote visits.
- d. At Visit 4, the investigator will evaluate the subject's eligibility to continue treatment with CVL-865 in the open-label extension trial CVL-865-SZ-002. If the investigator determines the subject is eligible for the trial, he/she will discuss with the subject if they would like to continue into Trial CVL-865-SZ-002. If the investigator determines the subject is eligible and the subject agrees to continue participation in Trial CVL-865-SZ-002, consent will be obtained and unique procedures for Visit 1 of Trial CVL-865-SZ-002 will be completed. Subjects who do not continue into Trial CVL-865-SZ-002 will begin the Taper Phase.

- e. Subjects who require early termination should begin the Taper Period at the time the decision is made to discontinue. All indicated procedures should be performed per protocol. If a subject discontinues early and it is inadvisable for them to taper IMP (after agreement from medical monitor), the subject should complete Visit 6 assessments approximately 30 days following the last dose of IMP.
- f. Individuals who do not meet the criteria for participation in this trial (screen failure) may be rescreened after consultation with the medical monitor. Rescreened subjects should receive a unique subject number for each screening.
- g. Unless procedure has been performed within 10 years prior to signing the ICF. This procedure, if necessary, should be conducted as soon as possible during the Screening/Baseline Period (per local guidelines) with the report available prior to randomization.
- h. A SIF/DRF will need to be completed by site personnel for every subject. This information will be faxed or emailed to TESC after the Screening Visit for review and approval. The SIF/DRF will be used by TESC to ensure that the seizures are classified accurately, the subject is appropriate for the trial, and will help to confirm the diagnosis.
- i. All subjects who normally take BZDs for seizure rescue will be required to have an individualized Rescue Protocol approved by TESC. The Rescue Protocol will be submitted along with the SIF/DRF and will describe what rescue treatment can be administered in the event the subject requires a BZD. It will also include different scenarios that will prompt immediate medical attention.
- j. Subjects cannot be enrolled until site personnel have received the TESC approval notification.
- k. All responses will be relative to the subject's condition at Day 1, prior to the first dose of IMP.
- 1. Full physical and neurological examinations should be completed at Screening Visit 4, and Visit 5/ET. The physical examination should include weight at all time points and height at the Screening Visit only. Physical and/or neurological examinations can be done at any time point during the trial at the investigator's discretion.
- m. The "Baseline/Screening" C-SSRS form will be completed for all subjects at Screening to determine eligibility and the "Since Last Visit" C-SSRS form will be completed at the Baseline Visit to ensure that the subject continues to qualify for the trial. The "Since Last Visit" C-SSRS form will also be completed at all visits after Baseline.
- n. Adverse events (serious and non-serious) and concomitant medications should be recorded from screening through the subject's last visit.
- o. For women of childbearing potential only. All positive urine pregnancy test results must be confirmed by a serum test. Pregnancy tests can be performed at any time during the trial at the discretion of the investigator if pregnancy is suspected.
- p. A urine drug screen is required at screening; see the exclusion criteria for exclusions based on the urine drug screen. The urine drug screen can be conducted at any time during the trial at the discretion of the investigator.
- q. With subjects maintaining their normal BID dosing routine, a single daytime blood sample for determination of plasma CVL-865 concentration will be collected at Visits 2, 3, 4, and 5. The date and time of the PK sample, as well as the time of ingestion of the morning dose of IMP (on the same day), will be recorded in the source documentation.
- r. One 5-mL sample for each individual adjunctive AED.
- s. Future biospecimen research sample is optional and is to only be collected if signed consent is obtained from the subject.

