## Follow-up Period:

See Figure 1 for a schematic of the trial design and Table 2 for the schedule of assessments.

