# 7.3 Individual Subject Discontinuation

After treatment assignment, a subject may stop treatment permanently for a variety of reasons. Treatment discontinuations may be initiated by a subject who is not satisfied with treatment or may become medically necessary due to AEs, required treatment with a disallowed medication or therapy, or other issues, as determined by the investigator.

Under certain circumstances, when subjects leave the trial early, dosing with the taper medication or continuing with the taper phase medication may be inadvisable. The decision not to taper the subject is upon agreement from the medical monitor. If the taper will not be utilized, then all assessments required at Visit 6 should be conducted 30 days following the last dose.

A subject will discontinue IMP for the reasons listed below:

- Any of the following AESIs
  - Hemoglobin <8 g/dL
  - $\circ$  WBC count <2.5 × 10^9/L
  - Neutrophil count  $< 1.5 \times 10^{9}/L$
  - Platelet count  $<100 \times 10^{9}/L$
- Failure to comply with trial procedures or dosing
- Withdrawal of consent

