#### • Investigator's discretion

If the subject temporarily interrupts or discontinues IMP due to an AE, the investigator or other trial personnel, will make every effort to follow the event until it has resolved or stabilized.

All subjects have the right to withdraw their consent from further participation in the trial at any time without prejudice. Subjects cannot withdraw consent for use of data already collected as part of the trial, but only for future participation. The investigator can also discontinue a subject's participation in the trial at any time if medically necessary. Unless the subject provides their written withdrawal of consent or there is other written documentation by the investigator confirming the subject's verbal intent to completely withdraw from the trial, subjects should be followed for all protocol-specified evaluations and assessments, if possible.

Complete withdrawal of consent requires a subject's refusal of ALL of the following methods of follow-up:

- Participation in all follow-up procedures specified in the protocol (whether inclinic, by telephone, or by an in-home visit).
- Participation in a subset of protocol specified follow-up procedures (by a frequency schedule and method, as agreed by subject and staff).
- Contact of the subject by trial personnel, even if only by telephone, to assess current medical condition, and obtain necessary medical or laboratory reports relevant to the trial's objectives.
- Contact of alternative person(s) who have been designated in source records as being available to discuss the subject's medical condition, even if only by telephone, mail, or e-mail (eg, family, spouse, partner, legal representative, friend, neighbor, or physician).
- Access to medical information from alternative sources (eg, hospital/clinic medical records, referring doctor's notes, public records, dialysis, transplantation or vital registries, social media sources).

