# 8.1 Screening and Baseline Assessments

All screening evaluations must be completed and reviewed to confirm that potential subjects meet all eligibility criteria. The investigator will maintain a screening log to record details of all subjects screened and to confirm eligibility or record reasons for screening failure, as applicable.

Procedures conducted as part of the subject's routine clinical management (eg, blood count) and obtained before signing of the ICF may be utilized for screening or baseline purposes provided the procedures met the protocol-specified criteria and were performed within the time frame defined in the Schedule of Assessments (Table 2).

As part of the screening procedures, a head magnetic resonance imaging or computed tomography scan will be completed to demonstrate no progressive structural abnormality, unless the procedure has been performed within 10 years prior to signing the ICF. This procedure, if necessary, should be conducted as soon as possible during the Screening/Baseline Period (per local guidelines) with the report available prior to randomization.

Subjects will be dispensed an electronic diary (eDiary) and be trained on its use at the screening visit. The presence or absence of all seizure types experienced by each subject will be recorded daily in the diary from the Screening Visit through Visit 6 (end of follow-up period). Site personnel should classify the seizure type based upon the description provided by the subject in the eDiary and, if needed, via further discussion with the subject. If a new seizure type occurs during the trial, the seizure category will be evaluated by the investigator and, if confirmed to be new, and not reported previously, it will be submitted to TESC for review. If seizures do not occur on any given day, lack of seizures is also recorded. Subjects will also record any use of BZDs.

As described in Section 5.1, a minimum of 8 focal onset (as defined in the 2017 ILAE Classification of Seizures [Fisher et al, 2017]), focal aware (except subjects with only focal aware seizures without a motor component), focal impaired awareness, or focal to bilateral tonic-clonic seizures during the 8-week Baseline Period with no 21-day period free of any of these seizure types should be confirmed by site personnel in order for the subject to be eligible for the trial.

A medical bracelet with subject and trial information will be dispensed at Visit 1.

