Study Day of Early Termination or Unscheduled Visit	Analysis Visit	Analysis Visit Target Day
1 or earlier	Baseline	
2 or greater	Day 71 (Visit 4)	71

Table 9:Visit Windows for Early Terminations and Unscheduled – mCIWA-B

Study Day of Early Termination or Unscheduled Visit	Analysis Visit	Analysis Visit Target Day
1 to 74 (on treatment, prior to Taper Phase)	Baseline	
1 to 82 (off treatment)	Day 78 (Contact)	78
83 to 89	Day 85 (Contact)	85
90 to 96	Day 92 (Visit 5)	92
97 to 110	Day 99 (Contact)	99
110 and higher	Day 120 (Visit 6)	120

Cerevel

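### After a stop without taper only Visit 6 is re-timed, so early stoppers have no timed mCIWA-B between early termination and about 30 days after last dose, and SAP Table 9 mixes off-drug with taper scores

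*Protocol*

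**What the plan says.** Withdrawal symptoms on the mCIWA-B are a listed secondary safety endpoint (Protocol section 3, Table 3). The schedule (Protocol Table 2, repeated as SAP Table 12) marks the scale at Visit 4 (Day 71), Days 78, 85 and 92, early termination (ET), a follow-up contact at Day ~99, and Visit 6 (Day 120).

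Subjects who stop early normally taper. Omitting the taper needs the medical monitor's agreement. In that case footnote e says "the subject should complete Visit 6 assessments approximately 30 days following the last dose of IMP", and Protocol section 7.3 says "If the taper will not be utilized, then all assessments required at Visit 6 should be conducted 30 days following the last dose". Neither mentions the Day ~99 contact. Two general rules also apply: "All indicated procedures should be performed per protocol" (footnote e) and "subjects should be followed for all protocol-specified evaluations and assessments, if possible" (section 7.3). Neither sets a new day for the contact.

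Protocol section 8.1 has the diary kept "from the Screening Visit through Visit 6 (end of follow-up period"), and the schedule entry "Collect final eDiary device" is marked at Visit 6. Under Follow-up Period, section 4.1 shows only "See Figure 1 for a schematic of the trial design and Table 2 for the schedule of assessments" in the text available for this review.

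SAP Table 9 keeps the contact as a fixed study-day time point, "Day 99 (Contact"). It assigns off-treatment ET and unscheduled scores from Days 1 to 82 to the Day 78 time point.

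**The concern.** A subject who stops without a taper loses drug with no step-down, so the first weeks off drug are when a withdrawal score is most informative. The plan moves the last visit closer for these subjects but leaves the intermediate contact on a calendar built for people who complete the taper. After an early stop, the contact arrives after follow-up has closed. A site would then most likely skip it, leaving ET and Visit 6 as the only scores.

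The SAP rule raises a second problem. The Day 78 row is meant to describe subjects stepping down through the taper. Adding scores taken after an abrupt stop, possibly many weeks earlier in study time, gives a summary that describes neither group.

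**Working it through.** **Inputs.** Visit 4 Day 71, taper 3 weeks, follow-up 4 weeks, contact Day ~99, visit windows of 3 days either side (Protocol Table 2 and section 4.1). Visit 6 without a taper: last dose + about 30 days (footnote e, section 7.3). Let D be the study day of last dose.

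**The plan's own schedule.** Visit 5 = 71 + 21 = Day 92. Visit 6 = 92 + 28 = Day 120. Both match Table 2. The contact lies 99 - 92 = 7 days after Visit 5 and 120 - 99 = 21 days before Visit 6.

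**When the contact no longer precedes Visit 6.** Re-timed Visit 6 = D + 30. The contact is on or after it when D + 30 <= 99, so D <= 69.
- D = 69: Visit 6 is Day 99, the same day as the contact.
- D = 70: Visit 6 is Day 100, one day after the contact.
- With 3 days allowed on both, the limit runs from (99 - 3) - (30 + 3) = Day 63 to (99 + 3) - (30 - 3) = Day 75.

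**Whether the taper-phase contacts could fill the gap.** If the general rules keep the Day ~99 mark, they can equally be read as keeping Days 78, 85 and 92. The first of these is on or after Visit 6 when D + 30 <= 78, so D <= 48.
- D before about 48: no nominal contact falls before Visit 6. Whether sites keep or skip the nominal days, nothing is timed between ET and about 30 days off drug.
- D from about 49 to 69: some of Days 78 to 92 could fall before Visit 6. For D = 57, Visit 6 is Day 87, and Days 78 and 85 are 21 and 28 days after last dose. The gap exists for these subjects only if sites treat those contacts as belonging to a taper that did not happen.
- With 3 days allowed on both, the Day 48 limit runs from (78 - 3) - (30 + 3) = Day 42 to (78 + 3) - (30 - 3) = Day 54.

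**SAP Table 9.** An off-treatment ET score on Day 20 goes to target Day 78, which is 78 - 20 = 58 days away. In the same row, completers on active drug who did not enter the extension are taking 17.5 mg or 5 mg BID (Protocol Table 4). An ET score taken while still on drug and before any taper goes to the Baseline row instead, so the mixing concerns off-drug scores only.

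**The proposed timing.** A contact at D + 7 comes (D + 30) - (D + 7) = 23 days before Visit 6 for every D. For D = 28, the contact is Day 35 and Visit 6 is Day 58.

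**The case against.** The best reply is that nominal days in Table 2 assume completion. Early terminators who do taper start at the time of the decision, so they cannot follow Days 78 to 120 as calendar days either. A sensible site would therefore read post-treatment contacts as relative to stopping. The mark ~99 is itself approximate, and no site would call a discharged subject weeks after Visit 6. That last point stands: a reader might infer calls long after follow-up has closed, but the documents make Visit 6 the end, and a skipped call is the likelier result. The relative reading is reasonable, but it is not written, and an untapered subject has no taper or Visit 5 from which to count.

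A reader might also infer that everyone with a last dose up to Day 69 lacks an interim score. The documents do not support that, because the same general rules may keep Days 78 to 92 for later stoppers.

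The Follow-up Period paragraph is nearly empty in the text reviewed, whereas the parallel Screening and Treatment paragraphs are full. A timing rule may have stood there.

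Finally, Protocol section 8.3.5 presents the scale as suited to tapering rather than abrupt stopping, so sparse use after an untapered stop could be deliberate. This limits how such scores can be read. It does not justify placing them in a taper row.

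**Conclusion.** The point holds as a small gap. The visible text re-times Visit 6 and nothing else. For a last dose up to about Day 69, the Day ~99 contact falls on or after Visit 6 and would probably be skipped. Before about Day 48, no mCIWA-B is timed between ET and about 30 days off drug, whether the nominal-day contacts are kept or dropped. Separately, SAP Table 9 mixes scores after an abrupt stop with taper scores in the Day 78 row.

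This assumes that no rule stood in the Follow-up Period text and that sites do not re-time the contact on their own judgement.

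The impact is limited. Untapered stopping is an exception, and the number affected cannot be derived from the documents. The mCIWA-B summary is descriptive, with no test. ET and Visit 6 scores remain, and adverse events are recorded to the last visit. A reader might infer that withdrawal goes unmonitored or that the safety conclusion is at risk; the documents support neither. Nor is a missing change score a further defect: SAP 5.14.8 defines change from the last on-treatment assessment, so without one there is no change score.

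**What to change.** In footnote e and Protocol section 7.3, add one sentence each: for subjects who stop without a taper, the existing follow-up contact with mCIWA-B takes place about 7 days after the last dose. The reason is that this falls early after drug stops and well before the re-timed Visit 6. It should not be presented as an exact match to the planned schedule, because Protocol Table 4 starts a taper dose on Day 92, so the planned contact may be less than 7 days after the last dose.

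In SAP Table 9, add one rule: off-drug scores from untapered subjects are summarised or listed separately by days since last dose, not in the Day 78 row.

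The cost is one existing call moved, two sentences and one SAP rule. The downside is a small call burden and a need for caution in reading the scores, given how section 8.3.5 describes the scale. No taper decision or efficacy analysis changes.
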